9.1 Data Reporting

9.1.1 Method

This study will be monitored by the Clinical Data Update System (CDUS) version 3.0. Cumulative CDUS data will be submitted quarterly to CTEP by electronic means. Reports are due January 31, April 30, July 31 and October 31. Instructions for submitting data using the CDUS can be found on the CTEP web site (<http://ctep.cancer.gov/reporting/cdus.html>).

Note: All adverse events that have occurred on the study, including those reported through CTEP-AERS, must be reported via the monitoring method identified above.

9.1.2 Responsibility for Data Submission

N/A

10 Cooperative Research and Development Agreement (CRADA) / Clinical Trials Agreement (CTA)

N/A

11 CONCOMITANT MEDICATION/MEASURES

In the event that a subject has a reaction (allergic) to the radiotracer, all appropriate medical measures will be taken immediately. In rare instances, this may entail admission to the hospital for observation.

12 DATA COLLECTION AND EVALUATION

12.1 Data Collection

12.1.1 Clinical Data

All data will be kept secure. Personal identifiers will not be used when collecting and storing data. An enrollment log will be maintained in the regulatory binder/file which is the only location of personal identifiers with unique subject identification number.

Clinical data including summary and demographic data will be collected and entered into NCI CCR Database, C3D. Adverse events occurring during any scanning session will be recorded. Adverse events which are designated possibly, probably or definitely related to ¹⁸F DCFBC will also be recorded.

Imaging data will include storage of the reconstructed images and image derived parameters on a secure, password protected lab imaging database. Images may also be stored in the clinical

CC Protocol Number: 14-C-0140
Abbreviated Title: DCFBC in prostate cancer
Version date: 10/27/2015
CIP #: 9622

center PACS. The lab imaging database will be stored and maintained in the Molecular Imaging Program facilities. Personal identifiers will not be used when storing data.

NCI Molecular Imaging Program may exchange anonymized clinical data with working groups, and qualified investigators. The anonymized image data will be stored in an existing secure off-site imaging database (EXEC PACS) and these images may be shared with researchers at other institutions.

During the one year follow-up period, the patient's PSA levels and prostate cancer related medical history, biopsy results, imaging studies and will be collected (reports and CD copies of the imaging studies).

12.1.2 Safety Data

The following safety data will be collected and evaluated according to the Study Calendar (Section 8.1.1):

- Clinical laboratory variables: CBC, acute care panel, hepatic panel
- Vital signs: systolic and diastolic BP, heart rate, body temperature, and respiration rate
- Physical examination
- Injection site monitoring
- Pre-administration events (baseline signs and symptoms)
- AEs

SAEs will be recorded if they occurred as follows:

- After a subject first received ^{18}F DCFBC and throughout the subject's follow-up period,
- During the subject's follow up period, and for which a causal relationship to ^{18}F DCFBC cannot be ruled out.

Interpretation and follow-up of abnormal results will be done on a case by case basis in conjunction with the individual clinical situation. Any clinically significant abnormal finding, or change in one that represents a worsening from baseline, is an AE. Once a decision is reached to report a finding as an AE, the investigator is required to follow the procedure described for AE notification.

12.1.3 Imaging Data

Extracted imaging data include:

- (1) PET imaging data will include SUV for each region of interest
- (2) All image data will be stored on a secure server, with access limited to credentialed users. This will permit flexible numeric raw data extraction for quantitative analysis and creation of summary data reports.

CC Protocol Number: 14-C-0140
Abbreviated Title: DCFBC in prostate cancer
Version date: 10/27/2015
CIP #: 9622

- (3) Anonymized image data from this study will be stored in a secure database that it is administered by the Cancer Imaging Program, NCI. The data may be shared with research collaborators to improve upon current methods of image analysis. The database is password protected and access is only given to qualifying collaborators.

Imaging findings for Na¹⁸F PET/CT will be dictated into the PACS system similar to other clinical radiologic studies, but dictations for ¹⁸F DCFBC PET/CT will only reflect the radiotracer dose, injection site and a statement indicating that the scan is for research purposes only.

12.2 Toxicity Criteria

The following adverse event management guidelines are intended to ensure the safety of each patient while on the study. The descriptions and grading scales found in the revised NCI Common Terminology Criteria for Adverse Events (CTCAE) version 4.0 will be utilized for AE reporting. All appropriate treatment areas should have access to a copy of the CTCAE version 4.0. A copy of the CTCAE version 4.0 can be downloaded from the CTEP web site (http://ctep.cancer.gov/protocolDevelopment/electronic_applications/ctc.htm#ctc_40).

13 Biospecimen Collection

13.1 Tissue Samples (Arm 1)

All tissue specimens (slide specimens) will have been obtained during the standard of care radical prostatectomy or biopsy under the NIH routine clinical protocol (part of the eligibility criteria for Arm 1) which includes: barcoding and labeling as follows:

Tissue samples will be shipped to a core biomarker laboratory analysis of PSMA expression by immunohistochemistry. Additional exploratory biomarker assessments may be conducted on tissue specimens to provide further information regarding correlation of tumor hypoxia and uptake of ¹⁸F DCFBC depicted by PET/CT.

Following completion of the core biomarker laboratory assessments, the PI, lead associate PI, one of the associate PIs or an appropriate designee will be responsible for collection of tissue specimens from the laboratories and return of specimens to NCI.

Upon return of specimens to the NCI and following completion of this study, samples will remain in storage at NCI. Access to these samples will only be granted following IRB approval of an additional protocol, granting the rights to use the material.

If, at any time, a subject withdraws from the study and does not wish for their existing samples to be utilized, the individual must provide a written request. Following receipt of this request, the samples will be destroyed (or returned to the patient, if so requested), and reported as such to the IRB. Any samples lost (in transit or by a researcher) or destroyed due to unknown sample integrity (i.e. broken freezer allows for extensive sample thawing, etc.) will be reported as such to the IRB.

CC Protocol Number: 14-C-0140
Abbreviated Title: DCFBC in prostate cancer
Version date: 10/27/2015
CIP #: 9622

Sample barcodes are linked to patient demographics and limited clinical information. This information will only be provided to investigators listed on this protocol, via registered use of the Patient Sample Data Management System (PSDMS). It is critical that the sample remains linked to patient information such as race, age, dates of diagnosis and death, and histological information about the tumor, in order to correlate genotype with these variables.

13.2 Blood Samples

Blood samples will be collected for screening and on-study clinical laboratory safety assessments. All blood samples will be processed and handled in accordance with standard laboratory procedures. All samples will be analyzed at the NCI Clinical Center laboratory.

14 STATISTICAL CONSIDERATIONS

14.1 Primary Analysis

This is a single site three-arm pilot study, where prostate cancer patients are enrolled into different arms according to their disease types: localized (Arm 1), recurrent (Arm 2) or metastatic (Arm 3). The primary objective of this study is to assess the ability of ^{18}F -DCFBC to identify sites of localized, recurrent and metastatic prostate cancer. To achieve this goal, ^{18}F -DCFBC PET/CT and conventional imaging will be used to identify positive suspected sites, and the proportion of positive concordance will be used to assess the performance of ^{18}F -DCFBC. In a recent study (Cho et al., 2012), 32 positive suspected sites in five prostate cancer patients with metastasis were identified by ^{18}F -DCFBC PET/CT with 21 concordant on both ^{18}F -DCFBC PET/CT and conventional imaging. At the individual level, the number of positive suspected sites ranged from 2 to 12 with the patient-specific concordance rate ranging from 0 to 100%. The overall concordance rate which was the average of individual-specific estimates across patients equaled 64% with corresponding standard deviation equal to 43%. For the new study, assume that for patients in Arm 1 and Arm 3, the mean concordance rate is 70% with 43% standard deviation as observed in Cho et al. With 12 evaluable patients in Arm 1, the 90% expected confidence interval for the mean concordance rate is (0.50, 0.90). With 20 evaluable patients in Arm 3, the 90% expected confidence interval for the mean concordance rate is (0.54, 0.86). For patients in Arm 2 (recurrent disease), it is unlikely to identify suspected lesions by conventional imaging at the baseline. These patients will be followed according to the protocol.

Amendment E Addendum:

Sensitivity of ^{18}F -DCFBC uptake in prostate cancer patients in Arm 2 is evaluated by its ability in differentiating mean values of PSA between PET-CT positive and PET-CT negative patients. To this end, the current study with sample size 35 for Arm 2 is under-powered to detect a sizeable mean difference in PSA between the two groups. Based on the preliminary data of the study, log-transformed PSA is approximately normally distributed with standard deviation equal to 1.3. Assume 1:2 allocation of PET-CT negative vs. PET-CT positive

CC Protocol Number: 14-C-0140
Abbreviated Title: DCFBC in prostate cancer
Version date: 10/27/2015
CIP #: 9622

patients. The current study has only 48% power to detect a 2.5-fold geometric mean ratio in PSA between the two groups at the 5% significance level using a two-sided Wilcoxon test. To achieve 80% power, 26 PET-CT negative and 52 PET-CT positive patients are required. These results are based on 2000 Monte-Carlo samples from the normal distributions. Under the alternative hypothesis, $\log(\text{PSA})$ is assumed to follow a normal distribution with mean (SD) equal to 0.06 (1.3) and 0.98 (1.3) for the PET-CT negative and PET-CT positive group, respectively. The mean difference of 0.92 ($=0.98-0.06$) in log scale of PSA corresponds to a 2.5-fold geometric mean ratio in the original scale.

In order to allow for the possibility of a small number of unevaluable patients, the accrual ceiling will be set at 15, 85 and 25, yielding a target ceiling of 125 patients for this study.

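### Section 14.1's 90% intervals for Arms 1 and 3 use the normal quantile with 12 and 20 patients, so the stated precision is slightly too favourable (minor)

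*Combined protocol and SAP*

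**What the plan says.** Section 14.1 (Primary Analysis) describes the trial as a pilot: "This is a single site three-arm pilot study". The primary measure in Arms 1 and 3 is each patient's rate of positive concordance between the tracer scan and conventional imaging, averaged over patients.

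The planning values come from a published study of the same tracer in five patients with metastatic disease. There the mean of the patient-specific rates "equaled 64% with corresponding standard deviation equal to 43" per cent, and individual rates ran from 0 to 100%. For this trial the plan assumes that "the mean concordance rate is 70% with 43% standard deviation", and derives two intervals:

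- Arm 1 (n = 12): "the 90% expected confidence interval for the mean concordance rate is (0.50, 0.90").
- Arm 3 (n = 20): the corresponding limits are 0.54 and 0.86.

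The section does not say which quantile was used, and it names no interval method for the final analysis. It sets no required half-width, null value or decision threshold for these intervals. Section 14.4 repeats the target numbers without further support, and the power calculation in the Amendment E addendum concerns Arm 2 only.

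**The concern.** The printed limits match a normal-quantile interval. That treats 0.43 as the known SD, yet the value comes from five patients, and the trial's own interval will rest on an SD estimated from 12 or 20. The usual interval for a mean then takes its quantile from the t distribution on n − 1 degrees of freedom, which is larger.

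Two things are at stake, both modest. First, these intervals are the only quantitative support for the sizes of Arms 1 and 3, so a reader is told to expect a little more precision than the assumptions give. Second, since no other interval method is named, an analyst could copy the construction and report nominal 90% intervals that cover somewhat less often.

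**Working it through.** **Inputs (all from section 14.1).** Mean m = 0.70; SD s = 0.43; n = 12 in Arm 1 and n = 20 in Arm 3; two-sided 90% confidence.

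**Step 1. Standard errors, s/√n.**
Arm 1: 0.43/√12 = 0.1241.
Arm 3: 0.43/√20 = 0.0962.

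**Step 2. Reproduce the plan's figures with the normal quantile, m ± 1.645 × s/√n.**
Arm 1: 1.645 × 0.1241 = 0.204, giving (0.496, 0.904), which rounds to (0.50, 0.90).
Arm 3: 1.645 × 0.0962 = 0.158, giving (0.542, 0.858), which rounds to (0.54, 0.86).
Both stated intervals are reproduced.

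**Step 3. Replace the quantile with t on n − 1 degrees of freedom.**

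| | t quantile | Half-width | Interval | Change in half-width |
|---|---|---|---|---|
| Arm 1 (11 df) | 1.796 | 0.223 | (0.477, 0.923) | 0.223/0.204 = +9% |
| Arm 3 (19 df) | 1.729 | 0.166 | (0.534, 0.866) | 0.166/0.158 = +5% |

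Each limit moves by about 0.02 in Arm 1 and 0.01 in Arm 3.

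**Step 4. Check other readings.** If the t half-width is based on the expected value of the sample SD, which is slightly below 0.43, the intervals are (0.482, 0.918) and (0.536, 0.864). The second rounds to the plan's Arm 3 figure, but the first does not round to its Arm 1 figure. A 95% normal interval gives (0.457, 0.943) and (0.512, 0.888). Of the constructions tried, only the 90% normal quantile matches both arms.

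**Step 5. Coverage if the normal construction were used with an estimated SD.** Under normally distributed patient rates:
n = 12: P(|t₁₁| < 1.645) = 87.2%.
n = 20: P(|t₁₉| < 1.645) = 88.4%.

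**Step 6. Coverage with bounded rates.** Patient rates lie between 0 and 1. With mean 0.70 the SD cannot exceed √(0.70 × 0.30) = 0.458, so 0.43 implies rates piled up near 0 and 1. A simulation that assumed beta-distributed rates with mean 0.70 and SD 0.43 (200,000 samples for each n) gave:

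| n | Normal quantile | t quantile |
|---|---|---|
| 12 | 86.3% | 88.2% |
| 20 | 87.4% | 89.1% |

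The t quantile is better in both arms but does not fully restore 90%.

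**Step 7. The difference in patients.** To keep the unrounded half-widths of 0.204 and 0.158 with t would take 14 and 22 evaluable patients. To keep the rounded ones of 0.20 and 0.16 would take 15 and 22.

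**The case against.** The strongest defence is that nothing was miscalculated. The plan fixes both the mean and the SD by assumption, and its intervals follow from those inputs. Treating an assumed SD as known is an ordinary planning convention, and section 14.3 does the same: with SD 0.30 and 8 patients, 0.1/(0.30/√8) = 0.94, which gives its 83% and 17%. This stands as a description of how the figures arose. However, section 14.1 does not say that it uses an approximation, and at 11 degrees of freedom the difference shows at the two decimals printed.

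A second defence is that nothing turns on the limits. This also stands. There is no precision target, and the futility rule in section 14.3 uses a different quantity, the PET-positive rate among conventionally identified sites, with a cut-off of 60% on the point estimate.

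A third is that uncertainty in the SD is larger than the choice of quantile. This is right as well. Under normality, a rough 90% lower limit for an SD estimated from five patients is 0.43 × √(4/9.49) ≈ 0.28, and the ceiling is 0.458. Over that range the t half-width at n = 12 runs from about 0.145 to 0.24. Because 0.43 is close to its maximum, the intervals actually obtained may be narrower than stated. That is a reason to call the intervals conditional on the SD. It does not support 1.645.

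The accrual ceilings do not settle the matter either. The plan says "the accrual ceiling will be set at 15, 85 and 25", but those extra places are an allowance for unevaluable patients and do not guarantee extra evaluable ones.

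**Conclusion.** The point holds as a minor correction. At the assumed mean of 0.70 and SD of 0.43, the stated intervals are too narrow for an SD that must be estimated: about (0.48, 0.92) instead of (0.50, 0.90) in Arm 1, and about (0.53, 0.87) instead of (0.54, 0.86) in Arm 3. If the true SD is clearly smaller than 0.43, the trial's intervals could be narrower than those printed.

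A reader might infer that the design fails to deliver its promised precision, or that Arms 1 and 3 need more patients. The documents do not support that: they promise no half-width, the shift is 0.01 to 0.02 per limit, and no decision uses the intervals. A reader might also infer that the trial's reported intervals will under-cover. That follows only if the final analysis uses the normal quantile with an estimated SD, and section 14 does not commit to it. The coverage figures of about 87% and 88% also assume normally distributed patient rates.

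**What to change.** In section 14.1:

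- Restate the expected 90% intervals as (0.48, 0.92) for Arm 1 and (0.53, 0.87) for Arm 3, and say that they use the t quantile on 11 and 19 degrees of freedom.
- Say that both are conditional on an SD of 0.43 taken from five patients.
- Name a t-based 90% interval for the final mean concordance rate in each arm, with a bootstrap interval over patients as a sensitivity check, because the rates are bounded and t coverage may still fall slightly below 90%.

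This costs a few sentences. Sample sizes, accrual ceilings and the futility rule stay as they are. The only downside is slightly less favourable stated precision.

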Much interest has centered on prostate specific membrane antigen (PSMA) as a target for imaging and therapy. Also known as Glutamate Carboxypeptidase II (GCPII) in the central nervous system, PSMA is a type II cell surface membrane glycoprotein receptor found in almost all prostate cancers, especially in advanced, hormone-independent and metastatic disease. It can also be found in the neovasculature of nearly all solid tumors. [1, 2] It is also seen in normal prostate, small bowel, proximal renal tubules, salivary glands and brain but at 100 to 1000 fold lower expression. [3] This normal expression appears to occur within luminal sites which is advantageous in formulating specialized antibodies because they do not need to cross intact basement membranes and tight junctions to bind. Another attractive feature of PSMA is that it does not appear to be secreted in serum, unlike PSA [4]; therefore imaging background due to organ perfusion will be less of an issue. Important to drug development, PSMA bound antibodies undergo internalization through clathrin coated pits. [5] This would give time for targeted imaging once any background activity and non-specific binding clears. These unique characteristics make PSMA a desirable target.

Monoclonal antibodies have been developed against PSMA, but the first agent, ¹¹¹In Prostascint, targets an intracellular epitope that is inaccessible in viable tumor cells which is one factor contributing to its lack of clinical utility.[6] More promising antibodies have been engineered with binding sites to the extracellular domain such as J591 and IgG monoclonal antibodies such as ⁶⁴Cu-3/A12. [7]

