3 PATIENT SELECTION

3.1 Eligibility Criteria

- 3.1.1 Subject is ≥ 18 years old
- 3.1.2 Platelet count $> 50,000/\text{mm}^3$
- 3.1.3 Eastern Cooperative Oncology Group (ECOG) Performance score of 0 to 2.
- 3.1.4 Ability to provide informed consent. All subjects must sign an informed consent form indicating their understanding of the investigational nature and risks of the study before any protocol-related studies are performed.
- 3.1.5 Categories
 - 3.1.5.1 ARM 1 only
 - 3.1.5.1.1 For patients with presumed localized disease (any T, N0, M0), a multiparametric MRI (standard of care at the NIH Clinical Center) must be performed within 4 months of the ^{18}F -DCFBC injection with findings suggestive for prostate cancer and a prostate lesion at least 6mm or greater. Must have histopathologic confirmation of prostate cancer prior to ^{18}F -DCFBC imaging.
 - 3.1.5.2 ARM 2 only:
 - 3.1.5.2.1 For patients status post radiation therapy for prostate cancer, any PSA increase from post radiation therapy nadir

OR

- 3.1.5.2.2 For patients status post prostatectomy, a PSA ≥ 0.2 ng/ml
- 3.1.5.2.3 Nonspecific or no evidence for disease on standard imaging modality
- 3.1.5.3 ARM 3 only:
 - 3.1.5.3.1 Patients must have identifiable metastatic disease on at least 1 clinically indicated imaging modality. If only soft tissue metastasis, one lesion must measure at least 6mm or greater. Patients must have confirmation of prostate cancer prior to ^{18}F -DCFBC imaging.

Note: A patient who is eligible for one arm, subsequently may cross-over into a different arm.

CC Protocol Number: 14-C-0140
Abbreviated Title: DCFBC in prostate cancer
Version date: 10/27/2015
CIP #: 9622

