Patients in Arm 2 who have had a prostatectomy may have a 2 or 3 lumen urinary catheter inserted to improve visualization of the bladder and adjacent anatomy during imaging. The urinary catheter is inserted prior to injection and is removed once all scans are completed. The 3 lumen catheter will be used to irrigate and empty the bladder during the scan. One lumen is used to inflate the balloon to secure the catheter in the bladder, the second lumen allows for continuous drainage of urine from the bladder during imaging and the third lumen allows for inflow of fluids. The catheter will be attached to an irrigation system that will allow for better visualization of the bladder and adjacent anatomy.

After the patient is injected with the radiotracer, the bladder will be filled with up to 500cc of saline via the third inflow arm of the urinary catheter. The outflow arm is attached to the drainage bag which has a clamp. The clamp on the drainage bag will be closed to allow for collection of the urine in the bladder. Approximately ten minutes before the patient is scanned the clamp on the drainage bag will be opened to allow for drainage of the bladder. The clamp will remain open during the imaging session to allow for continuous drainage of the bladder. This procedure will be repeated prior to the 2 hrs post-injection scan. Once all scans are completed the catheter will be removed.

A 2 lumen catheter will be used in lieu of the 3 lumen catheter to keep the bladder empty, if the patient cannot tolerate the insertion of a 3 lumen catheter.

If a patient is not able to tolerate catheter placement, they will be asked to empty their bladder frequently during the PET uptake phase and immediately prior to whole body PET/CT imaging.

CC Protocol Number: 14-C-0140
Abbreviated Title: DCFBC in prostate cancer
Version date: 10/27/2015
CIP #: 9622

A corresponding low dose CT scan for attenuation correction and co-registration purposes will be performed prior to each PET image (i.e. 1-single bed position including the prostate bed, and 2 whole body (1 each for the 1-hr and 2 hr images). All whole body ^{18}F DCFBC PET/CT images will be obtained from the top of the skull down to the thighs.

4.4.1 Summary of scanning procedure:

1. IV placement
2. If not previously drawn within 30 days of ^{18}F DCFBC, blood will be drawn for PSA measurement
3. Subject asked to void (Arm 2 patients will receive a urinary catheter which will be removed once all imaging is completed).

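### The pooled, unstratified Arm 2 comparison of PSA by scan result can be confounded by prior treatment and catheter use, in either direction

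*Combined protocol and SAP*

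**What the plan says.** **Entry.** Section 3.1.5.2 admits men to Arm 2 by either of two PSA rules. After radiation the rule is "any PSA increase from post radiation therapy nadir", with no numeric floor. The alternative is "For patients status post prostatectomy, a PSA ≥ 0.2 ng/ml". The two are joined by OR.

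**Scan technique.** Section 4.4 states: "Patients in Arm 2 who have had a prostatectomy may have a 2 or 3 lumen urinary catheter inserted". The step list in 4.4.1 says without restriction that Arm 2 patients will receive one. Section 2.3 (Amendment E Addendum) reports that the first 10 Arm 2 men were scanned without irrigation catheters and that this explains some of the findings.

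**Analysis.** Under section 14.1, Arm 2 sensitivity "is evaluated by its ability in differentiating mean values of PSA between PET-CT positive and PET-CT negative patients". One comparison is planned, "at the 5% significance level using a two-sided Wilcoxon test", with a single log-PSA SD of 1.3. The size is justified by: "To achieve 80% power, 26 PET-CT negative and 52 PET-CT positive patients are required". Neither 14.1 nor 14.2 names a stratum, covariate or subgroup for Arm 2. Section 4.2 is titled as stratification but only lists the arms.

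**Purpose.** Section 2.3 says the expansion is meant to define sensitivity as a function of PSA, as a benchmark for the next agent.

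**The concern.** PSA is the variable being compared, and the entry rules constrain it differently in the two prior-treatment groups. The protocol itself says that scan positivity depends on technique, and technique varied within the arm: over time for certain, and by prior treatment if section 4.4 governs. If prior treatment or catheter use is related to both PSA and the chance of a positive scan, the scan-positive and scan-negative groups will differ in treatment mix, and part of the PSA difference will come from that mix.

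Two things are at stake. The test may reject when PSA and scan result are unrelated within each group, or miss a relation that exists. And the result would depend on the proportion of post-radiation men who happened to enrol, so it would not carry over to a cohort of the next agent with a different proportion.

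**Working it through.** **1. The plan's own figure.** Inputs from 14.1: log-PSA means 0.06 and 0.98 (difference 0.92, which "corresponds to a 2.5-fold geometric mean ratio in the original scale"), SD 1.3, groups of 26 and 52, two-sided 5%.
- Normal approximation: SE = 1.3 × √(1/26 + 1/52) = 0.312; 0.92/0.312 = 2.95; power = Φ(2.95 − 1.96) ≈ 84%.
- Simulated Wilcoxon test: 80% to 81%, against 80% stated.
- At the former size of 35: 46% (12/23) to 47% (12/24), against 48% stated, within the error of 2,000 draws.

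The power calculation reproduces.

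**2. How pooling creates a difference.** Let *r* be the post-radiation share, *δ* the log-PSA difference (post-radiation minus post-prostatectomy), and *p*R and *p*P the positivity in each group. With no PSA-scan relation inside either group:

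pooled log ratio = *δ* × [P(radiation | positive) − P(radiation | negative)]

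If *p*R = *p*P the bracket is zero, and the pooled test keeps its 5% level even with a 4-fold PSA gap (simulated 5%).

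**3. Numbers.** The documents give none of *r*, *δ*, *p*R or *p*P, so all of these are assumptions.
- *r* = 0.30, *δ* = 1.0, 85% vs 55%: overall positivity = 0.255 + 0.385 = 0.64 (20/31 = 0.65 was observed). Bracket = 0.255/0.64 − 0.045/0.36 = 0.398 − 0.125 = 0.273. Ratio = exp(0.273) ≈ 1.31.
- *r* = 0.40, *δ* = log 4 = 1.386, 85% vs 55%: bracket = 0.34/0.67 − 0.06/0.33 = 0.326. Ratio = exp(0.451) ≈ 1.57.
- *r* = 0.50, *δ* = 1.5, 90% vs 50%: bracket = 0.45/0.70 − 0.05/0.30 = 0.476. Ratio = exp(0.714) ≈ 2.04.

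Simulated rejection at N = 78 with no relation inside either group:

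| Assumed inputs | Pooled Wilcoxon | Apparent ratio | Stratified |
|---|---|---|---|
| 20%, *δ* 0.7, 75% vs 62% | 5% | 1.06 | about 5% |
| 30%, *δ* 0.7–1.0, 75% vs 60% | 6% | 1.11–1.14 | about 5% |
| 30%, *δ* 1.0, 85% vs 55% | 13–15% | 1.30–1.33 | about 5% |
| 40%, *δ* 1.39, 85% vs 55% | 24% | 1.56 | 5% |
| 40%, *δ* 1.39, 55% vs 75% | 13% | 0.74 | 5% |
| 50%, *δ* 1.5, 90% vs 50% | 60–63% | 2.03–2.04 | about 5% |

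The two 40% rows hold the within-group SD at 1.3; the others hold the total SD at 1.3.

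**4. Masking.** Take a true within-group difference of 0.92, *r* = 0.30, *δ* = −1.0, 85% vs 55%. The pooled difference is 0.92 − 0.273 = 0.647, a ratio of 1.91. With about 50 positive and 28 negative men, SE = 1.3 × √(1/50 + 1/28) = 0.307; 0.647/0.307 = 2.11; power ≈ Φ(0.15) ≈ 56%. The simulated Wilcoxon test gives 53%, and the stratified test 83% to 84%.

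**5. Cost of stratifying.** With no confounding, power is about 81% pooled and 79% to 80% stratified. In two confounded cases with the within-group SD held at 1.3, stratified power was 74% and 78%.

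**The case against.** **The sizes are invented.** No mix, PSA or positivity by prior treatment is given, and milder inputs leave the test at 5% to 6%. The only documented PSA difference is that post-radiation men have no floor, which permits lower PSA, whereas the large rejection rates above assume higher PSA. This stands: neither size nor direction can be settled from the documents.

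**The test answers its literal question.** Section 14.1 asks whether PSA differs by scan result in the pooled arm. In the simulated cases it does, so rejection is correct for that comparison. This also stands, and the 5% test is not an error. But section 2.3 wants sensitivity as a function of PSA as a benchmark, and the pooled contrast serves that poorly if the treatment mix drives it.

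**Technique by prior treatment is not established.** A reader might infer from 4.4 that only prostatectomy men are catheterised; 4.4.1 contradicts that. The firmly documented variation is over time (the first 10 men), which stratifying by prior treatment alone would not address.

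**Background uptake.** A reader might infer that the groups differ in background because section 2.1 says of PSMA: "It is also seen in normal prostate, small bowel, proximal renal tubules, salivary glands and brain". That sentence goes on to put such expression 100 to 1000 fold lower, and nothing compares irradiated glands with a prostatectomy bed. Nor do the criteria say that post-radiation men keep a prostate: a man irradiated after prostatectomy could enter under the radiation rule. The point does not rely on either inference.

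**A stratified test is not a sensitivity curve.** True, and 78 men over four PSA bands and two groups average 78/8 ≈ 10 per cell. Hence the added model, and the caution about sparse cells.

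**Conclusion.** The concern holds as a risk of confounding that the plan leaves unaddressed, not as a demonstrated bias. The documents establish two PSA entry rules in one arm, technique that varied and is said to affect findings, and a single comparison without strata or covariates. Under assumed inputs, the pooled test rejects in about 5% to 60% of trials with no within-group relation, and its power falls to about 53% in the masking case. The upper figure is the most extreme case tried. All of this requires prior treatment (or catheter use) to be related to both PSA and scan result.

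A reader might go further and conclude that the result would reflect prior treatment in place of tracer sensitivity. The documents do not support that. At 40% post-radiation and 85% versus 55% positivity, confounding alone would need a PSA gap of exp(0.92/0.326) ≈ 17-fold to produce the planned 2.5-fold ratio. Nor is the sample-size calculation wrong; it reproduces.

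The change is still worth making before analysis: the direction is unknown, so a caveat at reporting could not correct it, and prior treatment is already known from eligibility.

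**What to change.** In section 14.1:
- Make the Arm 2 test a van Elteren (stratified Wilcoxon) test by prior treatment, and state the stratum for men who had both prostatectomy and radiation.
- Add a sensitivity analysis, such as a logistic model of scan positivity on log PSA adjusted for prior treatment and catheter use. This covers the change in technique over time and speaks more directly to the aim in section 2.3.
- Tabulate scan positivity by PSA for each prior-treatment group. Show any men below 0.2 ng/ml separately, since they fall outside all the bands in section 2.3.

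Sections 4.4 and 4.4.1 must be reconciled on catheter use, and the technique actually used recorded for each man.

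Cost: a few sentences and one table. Power falls by about one point without confounding, somewhat more if one stratum is small, and some table cells will be sparse.
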